#### **Statistical Considerations and analysis**

##### ***Derived variables***

##### **Total number of positive cores**

The total number of positive cores observed during follow-up is calculated by adding the maximum number of positive cores observed in each of the right and left lobes.

##### **Time to stage progression**

The time to progression will be calculated from the date of the procedure to the date of stage progression defined as the earliest date of onset of one of the following events, whichever occurs the earliest:

- Extracapsular extension confirmed with tissue sampling

- Seminal vesical invasion confirmed with tissue sampling
- Metastasis based on tissue confirmation with biopsy or post-mortem evaluation
- Cancer-related death will be assessed based on tissue confirmation with biopsy or post-mortem evaluation.

Subjects with no documented stage progression will be censored at the date of the last available on study disease assessment.

#### **Time to additional radical therapy (Days)**

The time to additional radical therapy will be calculated from the date of treatment to the date of initiation of the first radical therapy. If a subject did not receive any additional radical therapy during the study then the time to additional radical therapy for this subject will be censored at the study termination date.

#### **Time since diagnosis (Months)**

The time since diagnosis will be calculated from the date of diagnosis to the date of treatment.

#### **Age**

Age (years) = (date of informed consent – date of birth) / 365.25 rounded to the lowest integer.

#### **Body Mass Index (BMI)**

BMI (kg/m^2) = Weight (kg) / (Height (m) \* Height (m)).

#### **Light Density Index (LDI)**

The Light Density Index (LDI) is defined, for each zone to be treated, as the ratio of the cumulative length of illumination tip of the fibres (in cm) per cubic centimeter of the targeted zone. It is calculated as:

TI = (Total length of illumination tip of the fibre) / treatment volume

Where:

- The Total length of illumination tip of the fibre is the sum of the length of each illumination tip of the fibres used during the procedure for the treated lobe or quadrant. The volume of the targeted zone is calculated precisely by the prostate MRI conducted pre-treatment.
- An LDI equal or superior to 1.0 should be achieved for each zone to be treated.

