6.2.3 Treatment Conditions

Treatment guidance will help to determine the number and position of laser fibers to be inserted, with the length of illumination necessary to achieve a Light Density Index ≥ 1 in the targeted tissue. In case of unilateral disease, focal treatment of one lobe will be applied. In case of bilateral disease (discovered at entry or during follow-up), bilateral treatment will be applied consecutively or simultaneously. Retreatment of lobes found positive for cancer at 3-months follow-up will be allowed, provided there is no sign of cancer progression in the treated lobe and the patient did not experience grade 3 or 4 adverse events.

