6.2.4 Definition of the Light Density Index (LDI)

The Light Density Index (LDI) is defined, for each zone to be treated, as the ratio of the cumulative length of illumination tip of the fibers (in cm) per cubic centimeter of the targeted zone. It is calculated as:

$$\text{LDI} = \text{Total length of illumination tips of the fibers (in cm)} / \text{Treatment volume (in cc)}$$

Where:

1. The total length of illumination tip of the fibers is the sum (in centimeters) of the length of each illumination tip of the fibers used during the procedure for the treated lobe.
2. The treatment volume (in cc) is calculated by the TOOGUIDE- TRUS software after delineation of the prostate by the investigator on the TRUS image.

3. An LDI equal or superior to 1.0 should be achieved for each zone to be treated.

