##### ***Efficacy population***

The efficacy population will include patients who complied with the protocol for inclusion criteria and exclusion and follow-up received the appropriate dose of TOOKAD® Soluble, LDI and energy delivered and underwent the VTP procedure, receiving the ascribed dose of TOOKAD® Soluble and light, had no major protocol deviations and provided data at the 12 month biopsy. A "major" protocol deviation is defined as one which, in the opinion of the PI, could importantly influence the result of the 12 months biopsy and which is adjudicated before the 12-month biopsy.

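### The SAP calculates LDI from the pre-treatment MRI volume, the protocol from the TOOGUIDE TRUS volume on which the fibres are planned, and the efficacy population requires an appropriate LDI without naming a number or a volume.

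*SAP*

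**What the plan says.** Both documents define LDI as total illuminated fibre length divided by the volume of the zone treated. They differ on where the volume comes from.

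- **Protocol 6.2.4:** "The treatment volume (in cc) is calculated by the TOOGUIDE- TRUS software after delineation of the prostate by the investigator on the TRUS image".
- **SAP, Light Density Index (LDI):** "The volume of the targeted zone is calculated precisely by the prostate MRI conducted pre-treatment".

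The threshold is the same in both. The protocol's sentence, "An LDI equal or superior to 1.0 should be achieved for each zone to be treated", is repeated in the SAP. Protocol 6.2.3 plans the fibres "with the length of illumination necessary to achieve a Light Density Index ≥ 1 in the targeted tissue", and protocol 2.2.5 bases the volume assessment for that planning on TRUS images.

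The numerators also differ slightly. The protocol sums the "length of each illumination tip of the fibers used during the procedure for the treated lobe"; the SAP refers to "fibres used during the procedure for the treated lobe or quadrant" and labels the result TI.

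LDI is used in two places. It is summarised descriptively (protocol 10.2.2.2; SAP, Treatment modalities). It is also a condition of the SAP efficacy population, whose members must have "received the appropriate dose of TOOKAD® Soluble, LDI and energy delivered". Protocol 10.2.2.4 sets the same condition for its per-protocol population. The SAP section on efficacy analysis runs all efficacy analyses, including the primary one, on the efficacy population.

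**The concern.** One index with one threshold has two denominators. The urologist chooses fibres to reach at least 1.0 on the TRUS volume, whereas the analyst following the SAP divides by an MRI volume. The two values agree only if the two volumes agree.

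Two things are at stake. The reported LDI would describe something other than what was planned and delivered in the operating room, even if no man is excluded. Membership of the primary analysis set could also depend on the imaging method, because the efficacy population calls for an appropriate LDI without saying what value qualifies or on which volume. In an open-label, single-arm trial, the rule for who is counted should leave no such choice open.

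**Working it through.** **Inputs from the documents.** LDI definitions and threshold of 1.0: protocol 6.2.4 and the SAP LDI section. Null rate 70%, assumed rate 83.6%, one-sided alpha 10%, power 80%, N = 44: SAP, Planned sample size. Success rule (lower bound of a one-sided 90% interval, rounded to 0.01, at least 70%; 35 of 44): SAP, Primary efficacy analysis. Neither document gives an MRI-to-TRUS volume comparison or a distribution of achieved LDI.

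**1. The plan's own figures.** With the normal approximation,

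n = [(z₀.₉₀·√(0.70·0.30) + z₀.₈₀·√(0.836·0.164)) / 0.136]² = 43.7, so 44, as the SAP states.

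The Clopper-Pearson one-sided 90% lower bound for 35/44 is 0.696, which rounds to 0.70 and passes. For 34/44 it is 0.672, which fails. The SAP's rule of 35 is reproduced. LDI is not an input to this sample size; it affects only who is counted.

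**2. How the denominator moves LDI.** The fibre length is the same in both calculations, so

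LDI(MRI) = LDI(TRUS) × V(TRUS) / V(MRI).

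A man at or above 1.0 on TRUS falls below 1.0 on MRI whenever V(MRI) > LDI(TRUS) × V(TRUS). The volume differences below are assumptions:

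| LDI on TRUS | MRI volume relative to TRUS | LDI on MRI |
|---|---|---|
| 1.00 | +5% | 1/1.05 = 0.95 |
| 1.00 | +10% | 1/1.10 = 0.91 |
| 1.00 | +20% | 1/1.20 = 0.83 |
| 1.20 | +10% | 1.20/1.10 = 1.09 |
| 0.90 | −10% | 0.90/0.90 = 1.00 |

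Reclassification can go either way, and it depends on how close to 1.0 the man was planned.

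**3. Illustrative shares.** Assume that the log of the MRI/TRUS volume ratio is normal with mean 0 and SD between 0.05 and 0.20. The chance that LDI(MRI) is below 1.0 is then 1 − Φ(ln LDI(TRUS) / SD):

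- LDI(TRUS) = 1.00: 50% at any SD.
- LDI(TRUS) = 1.10: 3% to 32%.
- LDI(TRUS) = 1.20: 0% to 18%.

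These figures show sensitivity to the assumption. They do not estimate what will happen in this trial.

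**4. What one exclusion does at the boundary.** An exclusion removes a man from the denominator and, if he responded, from the numerator too. From 35/44 (79.5%):

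- Excluding a responder gives 34/43 = 79.1%, a change of −0.5 points. The lower bound is 0.690, which fails.
- Excluding a non-responder gives 35/43 = 81.4%, a change of +1.9 points. The lower bound is 0.715, which passes.

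From 34/44, excluding a non-responder also gives 34/43, which still fails.

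**The case against.** The strongest reply is that the SAP nowhere says a man with MRI-based LDI below 1.0 is excluded. Its efficacy population repeats the protocol's per-protocol wording almost unchanged and begins with compliance with the protocol, so the natural benchmark is the protocol's TRUS-based LDI. The statement that 1.0 should be reached reads as planning language, and the only explicit use of the SAP-derived LDI is a descriptive summary. This stands in part: exclusion at an MRI-based 1.0 is an inference. It does not remove the conflict, because the SAP's only definition of LDI is the MRI-based one and the criterion does not say which definition applies.

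It can also be said that the principal investigator's judgement on major deviations, adjudicated before the 12-month biopsy, prevents arbitrary exclusion. As written, that judgement covers major deviations; LDI is listed as a separate condition.

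A reader might infer more than the documents support:

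- **That each affected man moves the primary rate by about 2 points.** The change is −0.5 or +1.9 points, depending on whether he responded, and 35 is the cut-off only at N = 44.
- **That power falls by a definite amount.** The number excluded is unknown, and exact power is saw-toothed: 0.826 at N = 44, then 0.757, 0.801 and 0.722 at 42, 40 and 38 under the SAP's rule.
- **That the MRI is months old at treatment.** The interval from MRI to procedure is not fixed anywhere.
- **That the TRUS treatment volume is certainly on file.** Protocol 14.1.1 lists the TOOGUIDE TRUS report among the copies sent to the sponsor but does not state its contents. Protocol 11.2 names power, energy and diffuser length among the items on the VTP report form, without naming volume.

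The SAP's mention of quadrants is clerical, since this protocol treats lobes.

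**Conclusion.** The concern holds as a definitional conflict with a possible effect on the primary analysis set. That the two denominators differ is certain from the text. It follows that an LDI table produced to the SAP will not show the index to which the fibres were planned.

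The effect on the efficacy population is possible but unquantified. It requires that the unstated criterion be read as 1.0 on the MRI volume, that the two volumes differ, and that some men were planned close enough to 1.0 for the difference to matter. The documents settle none of these. No directional bias in the primary result is claimed. The case for acting is that one exclusion can reverse the decision at the boundary (35/44 passes, 34/43 fails) and that the ambiguity is easily removed. Aligning the SAP is worthwhile, but the documents do not show that the trial's conclusion is compromised.

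**What to change.** 1. Reconcile protocol 6.2.4 and the SAP's LDI section to one volume source.
2. For the analysis variable and the efficacy-population condition, calculate LDI from the volume on which the procedure's LDI was planned, so that the variable measures adherence to the plan. First confirm that the TOOGUIDE TRUS report captures the treated-zone volume.
3. State in the efficacy-population definition the numeric LDI criterion and its volume source, and fix both before Month 12 results are known.
4. Show MRI-based LDI only as a sensitivity listing.
5. Remove or explain the reference to quadrants, and use one label for the index.

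The cost is a short SAP amendment and a check of existing procedure reports. If the planned volume proves not to have been captured, it would have to be retrieved from the treatment-guidance records. The change concerns analysis classification only; no clinical LDI target is proposed.

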#### **Baseline value**

Baseline value will be defined as the last reported value until the date of treatment.

For those patients with two biopsies at baseline the following definitions of baseline values will be applied:

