12. MRI

6.4.2 Visit 2 (V2): TOOKAD® Soluble VTP procedure

Subjects will come to the unit on the day of the procedure, having fasted per institutional standards in preparation for anaesthesia. After the TOOKAD® Soluble- VTP treatment, they will remain in the clinical unit under medical and nursing supervision for at least 6 hours after TOOKAD® Soluble infusion. The subject will be kept under medical surveillance in a dimmed room for at least 6 hours after the procedure and may be discharged in the evening of the procedure day. Depending on the duration of the anaesthesia and the patient condition, the investigator can decide to keep him hospitalised overnight. In this case, the patient may be discharged in the following morning. Further need for inpatient based hospital care will be based on the patient's condition and medical needs as determined by the treating physician. Post-procedure hospitalization is expected to vary from approximately 6 to 24 hours. If for any reason other than those listed above (i.e., distant home) the investigator decides to keep the patient overnight, such

reason is to be recorded in the CRF, and a mention is to be made that the patient could have been discharged in the evening of the procedure day.

Prior to Anaesthesia:

1. Concomitant medication
2. AEs recording
3. Vital signs (blood pressure, pulse rate and body weight)
4. Blood collection for laboratory testing and PSA testing

After anesthesia has been induced, anesthetic monitoring is to be done according to institutional clinical practice guidelines. Patients are to be placed in the lithotomy position and to remain in this position during the procedure. During the procedure, the patient's skin and eyes are to be protected from the operating room surgical lights with opaque drapes.

After the VTP procedure, the following procedures and assessments are to be made:

1. Recording of adverse events (AEs)
2. Performance of clinical examination
3. Assessment of concomitant medication
4. Blood samples for laboratory and PSA testing 4 to 6 hours following the procedure
5. Removal of catheter

The subject is then discharged from the hospital, unless there are medical reasons that require prolonged hospitalisation.

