8.3 Laboratory Assessments

Choice of the laboratory

A local laboratory will be used for safety biological parameters and PSA testing.

Laboratory examinations

The following laboratory tests should be prescribed at Visit 1 and their results should be available for eligibility assessment prior to the VTP procedure. If similar laboratory tests are available in the patient file before the patient is considered and approached for his entry in the study, the results of these test can serve as the eligibility assessment and do not need to be repeated, provided they have not been done more than 4 weeks before visit 1.

At any time during the study, for safety reasons, and when in the patient's best interest, additional tests may be performed at the discretion of the Investigator.

If one of the result of the laboratory tests (eg PSA levels) done after consent signature do not meet the inclusion/exclusion requirements, it can be repeated at the discretion of the investigator, but not more than twice.

Screening (V1) blood tests:

- Standard hematologic tests
- Standard blood chemistry tests
- Standard Blood Coagulation Tests

- Additional inclusion blood tests
- PSA

Blood tests to be taken during the during Visit 2 both before and after the TOOKAD® Soluble VTP procedure as well as taken 1, 3, 6, 12, 24, 36, 48 and 60 months after the VTP procedure:

- Standard hematologic tests
- Standard blood chemistry tests
- PSA

Standard hematologic tests:

Hemoglobin, Red cell count, M.C.V., Hematocrit, M.C.H., White cell count, Differential white cell count (%), Platelet count.

Standard blood chemistry tests:

Sodium, Potassium, Chloride, Bicarbonate, Calcium, Creatinine, Urea, Glucose, Total Protein, Albumin, Alkaline Phosphatase.

Standard Blood Coagulation Tests:

INR (pro-time), aPTT.

Additional inclusion blood tests:

Alanine Aminotransferase (ALAT/SGPT) and Aspartate Aminotransferase (ASAT/SGOT)

PSA:

Prostate Specific Antigen

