Quality of life is assessed using validated questionnaires. The IPSS comprises seven questions on the urinary symptoms plus one general question about the QOL related to urinary symptoms, whereas the IIEF comprises 15 questions. For both questionnaires, patients self-rate their responses: for the IPSS, using a six-point scale where 0 indicates 'none' or 'normal', whereas 5 indicates the worst response; for the IIEF, using a five- or six-point scale where 0 indicates 'no sexual activity', and 5 indicates the best response (questions 1 to 10), or where 1 indicates the worst response and 5 the best response (questions 11 to 15).

- Rate of adverse events following treatment

As described in section 9.1, adverse events will be recorded and reported descriptively. Events will be annotated and graded according to National Cancer Institute Common Toxicity Criteria version 4.03.

- Severe prostate cancer-related events: cancer extension to T3, metastasis or prostate cancer-related death

Stage progression to T3 disease (extracapsular extension or seminal vesical invasion), metastasis or cancer-related death will be assessed based on tissue confirmation with biopsy or post-mortem evaluation. Radiographic evidence of suspicious findings will not be utilized unless confirmed with tissue sampling.

- Use of secondary cancer therapies following VTP treatment

Patients who proceed to additional therapies for prostate cancer treatment such as radiation, surgery, hormone or chemo therapies will be documented. Adjunctive surgical or medical therapies that are not intended as cancer treatments but for management of post-treatment related events will be recorded under adverse event reporting and graded appropriately.

- Serum PSA measurements in ng/mL.

Patients blood will be drawn and PSA level determined at 1, 3, 6, 12 months and annually thereafter. Changes from baseline will be determined.

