**Demographic and baseline characteristics**

Demographic characteristics such as age, gender, ethnic origin, height, weight and BMI will be summarized. Specific baseline disease characteristics such as time since diagnosis, TNM staging, PSA, prostate volume, type of disease (unilateral/bilateral), total number of positive cores will be summarized.

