**Clinical laboratory evaluation**

Laboratory values will be individually listed by patient number. Values outside the laboratory reference ranges will be flagged on these individual data tables. The investigator will assess whether the values outside of the reference ranges are clinically significant or clinically non-significant. Lab abnormalities will be graded using the NCI Common Terminology Criteria for Adverse Events.

For those parameters that can be graded according to the NCI Common Terminology Criteria for Adverse Events, summaries of shift from baseline in toxicity grade to each post-baseline visit will be provided.

For those parameters that cannot be graded, frequencies of patients' transitions between normal and abnormal not clinically significant (NCS) and abnormal clinically significant (CS) categories will be tabulated.

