**Vital signs**

Descriptive statistics for raw and change from baseline at each planned assessment will be provided by treatment group for oral temperature, blood pressure and pulse rate using both the continuous measure and the proportion of patients outside the reference range ( $>38^{\circ}\text{C}$ ,  $>120/80$  and 60 – 100, respectively) and will be presented in a table.

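### The SAP's date-based baseline rule can take the PSA, hematology and chemistry sample drawn 4-6 hours after VTP as baseline, and on its other reading it discards the pre-anaesthesia sample

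*SAP*

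**What the plan says.** The SAP gives one general rule, under Baseline value: "Baseline value will be defined as the last reported value until the date of treatment". Separate rules follow for men with two baseline biopsies. Neither document defines baseline separately for blood tests or PSA.

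The protocol schedules two blood draws on the day of treatment. Section 6.4.2 lists, before anaesthesia, "Blood collection for laboratory testing and PSA testing". Among the post-procedure assessments it lists "Blood samples for laboratory and PSA testing 4 to 6 hours following the procedure". Section 8.3 confirms that hematology, chemistry and PSA at Visit 2 are taken "both before and after the TOOKAD® Soluble VTP procedure".

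These outputs use the baseline value:

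- SAP, Demographic and baseline characteristics: "Specific baseline disease characteristics such as time since diagnosis, TNM staging, PSA, prostate volume" are to be summarized.
- Protocol 10.4.1, for PSA: "Changes from baseline will be determined".
- SAP, Clinical laboratory evaluation: for gradable tests, "summaries of shift from baseline in toxicity grade to each post-baseline visit will be provided". Tests without a grade get tables of transitions between normal and abnormal categories.
- SAP, Vital signs: "Descriptive statistics for raw and change from baseline at each planned assessment".

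**The concern.** A baseline should be the last value the treatment could not have affected. Here the rule stops at a date, and two samples share that date, one on each side of the procedure. A programmer who keeps everything up to and including the treatment date and takes the last record will select the 4-6 hour sample for every man who has both.

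Day 7 has no blood tests (Protocol 6.4.3 and the Schedule of Events), so the 4-6 hour sample is the only scheduled acute laboratory result before Month 1. If it becomes baseline, a change that arose at the procedure no longer appears as a shift, and recovery from it appears as improvement. For PSA, whatever the procedure does to the value within hours is carried into every later change from baseline.

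**Working it through.** **No planned figure to reproduce.** This is a derivation rule, so the check is to apply it to the visit schedule, parameter by parameter.

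**Step 1: the two readings of *until*.**

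| Reading | Baseline for PSA, hematology, chemistry | Problem |
|---|---|---|
| Treatment date included | 4-6 hour post-VTP sample | Baseline is measured after treatment |
| Treatment date excluded | Visit 1, or a file result up to 4 weeks before Visit 1 (Protocol 6.4.1, 8.3) | The pre-anaesthesia sample is ignored, or is tabulated as post-baseline although it precedes treatment |

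Neither reading yields the pre-anaesthesia sample, and nothing in either document settles which one applies.

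**Step 2: which parameters are exposed under the inclusive reading.**

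| Parameter | Collected on treatment day after VTP? | Exposed? |
|---|---|---|
| PSA, hematology, chemistry | Yes (6.4.2, 8.3) | Yes |
| Vital signs | Measured before anaesthesia. After VTP a clinical examination is listed without naming vital signs, though the Visit 1 examination includes blood pressure and pulse | Only if recorded at that examination |
| IPSS, IIEF | No: entry, then Month 1 onward (7.2) | No |
| Coagulation, ALT/AST | No: screening only (8.3) | No |
| Biopsy variables | No: taken from pre-treatment biopsies | No |
| Primary endpoint | Uses no baseline value | No |

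**Step 3: re-treated men.** Protocol 6.4.10 allows one re-treatment, so these men have two treatment dates. The SAP does not say which is meant.

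**Step 4: effect on PSA change.** Let P be PSA before VTP, F the follow-up PSA, and k the ratio of the 4-6 hour value to P.

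- True percentage change = 100 × (F/P − 1).
- Change from the post-VTP baseline = 100 × (F/(kP) − 1).
- Error in ng/mL = (F − kP) − (F − P) = P − kP. F cancels, so a given man's error is the same at every follow-up visit.

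The documents give no 4-6 hour PSA values. Assume P = 6 and F = 3 for illustration only. The true change is 3 − 6 = −3 ng/mL, or −50%.

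| k (assumed) | 4-6 h PSA | Change, ng/mL | Change, % | Error, ng/mL |
|---|---|---|---|---|
| 0.8 | 4.8 | −1.8 | −37.5 | +1.2 |
| 1.0 | 6.0 | −3.0 | −50.0 | 0 |
| 1.25 | 7.5 | −4.5 | −60.0 | −1.5 |
| 1.5 | 9.0 | −6.0 | −66.7 | −3.0 |
| 2 | 12.0 | −9.0 | −75.0 | −6.0 |
| 5 | 30.0 | −27.0 | −90.0 | −24.0 |

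**Step 5: effect on the shift tables.** Take a test that is normal before anaesthesia, abnormal at 4-6 hours and normal again at Month 1. With the correct baseline the table shows a worsening on the treatment day and no shift at Month 1. With the post-VTP baseline the treatment-day worsening is absent and Month 1 shows an improvement.

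**The case against.** **The wording can be read innocently.** If *until* excludes the treatment date, no post-VTP value can be chosen. Context supports a pre-treatment intent: the protocol lists the 4-6 hour sample among the assessments after VTP, and the SAP contrasts baseline with post-baseline visits. This stands against saying that the rule does select the post-VTP sample; it only can. It does not rescue the rule, because the exclusive reading passes over the sample drawn immediately before treatment.

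**Acute toxicity would still be reported.** A reader might infer that acute laboratory toxicity would vanish from the safety report. The documents do not support that. The SAP lists every laboratory value by patient, flags those out of range, has the investigator judge clinical significance and grades abnormalities. Protocol 9.1 and 9.2 also count abnormal laboratory findings as adverse events, which the SAP tabulates. These outputs stand, but they do not correct the shift and transition tables.

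**Not every baseline table is exposed.** A reader might infer that all change-from-baseline summaries are distorted. Step 2 shows otherwise.

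**The direction for PSA is not known.** A reader might infer that the later PSA fall would be exaggerated. That needs a 4-6 hour value above the pre-VTP value, and no section reports one or says that VTP raises PSA. At a ratio of 1.0 there is no error, and at 0.8 the fall is understated.

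**The second PSA draw is less uniform than it looks.** The Schedule of Events gives the before-and-after footnote to hematology and chemistry at Visit 2 but marks PSA with a plain cross. Sections 6.4.2 and 8.3 both state the second PSA draw outright, so the point holds for PSA, and the discrepancy does not touch hematology or chemistry.

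**The stakes are limited.** PSA change is descriptive. It is a secondary objective in the SAP, but it is missing from the SAP's endpoint list and has no analysis section there. No test or success rule depends on it. This stands.

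**Conclusion.** The rule is faulty as written for PSA, hematology and chemistry. Read inclusively, it takes a post-treatment sample as baseline. Read exclusively, it ignores the sample drawn just before treatment. Under the inclusive reading, the baseline PSA summary, PSA change from baseline and the hematology and chemistry shift and transition tables would be biased, and the only scheduled acute laboratory result before Month 1 would drop out of the shift tables. Vital signs are at risk only if they are recorded at the post-VTP examination.

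The size for PSA cannot be computed from the documents. The range in Step 4 rests wholly on assumed values and includes no error at all. The bias also requires the post-VTP value to differ from the pre-VTP value.

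The consequence is confined to descriptive secondary and safety summaries. It is still worth correcting before programming, because the rule could reach every treated man with both samples.

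**What to change.** Replace the general sentence under Baseline value in the SAP with a rule to this effect: baseline is the last non-missing value obtained before the start of the first VTP procedure, that is, before anaesthesia, identified by sample time or by a pre/post-procedure label. Add that the 4-6 hour sample is the first post-baseline assessment and appears as such in the laboratory shift and transition tables and in the PSA summaries.

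Naming the first procedure also settles the baseline for re-treated men. If the pre-anaesthesia sample is missing, the rule falls back to the Visit 1 or file value. The biopsy-specific baseline definitions can stay as they are.

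The change costs one or two sentences in the SAP. It needs no new data and no change to the visit schedule, provided that the two Visit 2 samples can be told apart in the database by time or label, which should be confirmed.
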